KØBENHAVNS UNIVERSITET - TANDLÆGESKOLEN

Forsøgsprotokol Jf. GCP-enhedens protokolvejledning

(The main research protocol is developed based on the guidelines for Good Clinical Practice (GCP))

1. Title:

DIMOH: New **Di**gital **M**ethods for **M**onitoring **O**ral **H**ealth. An i*n vivo* assessment. Odontologisk Institut - Tandlægeskolen Det Sundhedsvidenskabelige Fakultet Københavns Universitet [name]

2. Objectives

The objectives of this study are *i*) to monitor the oral health of young people over a period of 12 months and *ii*) to assess the ability of a new intraoral scanner combining fluorescence (from emitted blue light) with 3D imaging to detect and monitor changes in the dental hard tissues *in vivo*.

a. Hypotheses

The working hypotheses of this study are:

- 1. The monitoring of oral health will benefit from using a new intraoral scanner combining fluorescence with 3D imaging.
- 2. The new intraoral scanner combining fluorescence with 3D imaging will aid dentists to identify changes in the dental hard tissues at earlier stages than the traditional diagnostic methods (*i.e.* visual-radiographic methods).

b. Background

Literature Review and Research Question

Currently, monitoring oral health relies mainly on the visual examination of the oral tissues by the dental professional, aided electively by radiographic or photographic images (1, 2). In the context of oral health, monitoring involves detecting changes, sometimes rather subtle, in the soft or hard oral tissues; such changes are associated with the development of oral diseases or ageing (3, 2). Through the course of their lives, people will experience changes in the level of gingiva, increments on the teeth surface due to calcification of biofilm, loss of mineral tissues due to caries or tooth wear, wear of restorative materials, or modification in the in the position or color of the teeth. The slow rate of change involved in some of these situations makes it extremely difficult for the human eye alone to identify them. It is even more challenging to accurately register and recall the original situation on the patient's follow-up visits. Clinical photographs are therefore used to aid the monitoring (4, 2); however, it is difficult to obtain comparable photographs from different points in time and the subjectivity involved in the process cannot be avoided.

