Different criteria are used in clinical practice to register and monitor changes in the oral tissues, according to the specific condition under investigation. While identifying significant changes is an easy task, the challenge lies particularly in identifying early, incremental changes. Regarding the detection of caries lesions, a number of initial lesions typically remain unnoticed when visual examination alone is used (5); or even when radiographs are employed, as the latter are not sensitive to early demineralization in enamel (6). Concerning tooth wear (*i.e.* erosion, abrasion, attrition), as the gradual mineral loss occurs progressively and irreversibly, it is usually only noticed when a significant amount of hard dental tissue is already lost (2). Additionally, minor changes on the gingival level, *e.g.* resulting from improper oral hygiene habits or yet an early inflammation of the periodontal tissues, may pass unnoticed to the dental personnel.

A promising clinical solution to overcome the challenges involved in the detection of early changes and monitoring of oral tissues is the use of 3D intraoral scans (7, 8). 3D scans obtained from gypsum models (*ex vivo*) have previously been used to identify changes of tooth position (9, 10), gingiva volume (11, 12), loss of mineral tissues (13) or wear of restorative materials (14). Although gypsum models offer information about volumetric changes (*e.g.* tooth

substance loss, movement of teeth, gingival level, stagnation of biofilm), the color information is lost. However, color is a valuable parameter for the previously mentioned clinical criteria as it is one of the parameters used to identify diseases (*e.g.* caries, gingivitis) or other oral conditions (*e.g.* tooth discoloration due to ageing, tooth whitening or discoloration of dental materials) (15, 2). Hence, obtaining 3D scans directly from the patients (*in vivo*) using intraoral scanners is desired, as these scans contain color information of the natural tissues. Additionally, by comparing 3D scans obtained from the same patients at different points in time, a less subjective and more reliable comparison of data is expected: the 3D scans can be overlapped and analyzed using specific software (9, 7, 16). Therefore, it is hypothesized that 3D intraoral scans can be used for more consistent monitoring of oral health in relation to clinical photographs or clinical records.

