The same clinical procedures will be followed on the follow-up examinations (3 or 6 months) as well as on the final examination (1-year follow-up). The diet history, the oral hygiene habits questionnaire and the BW radiographs will be repeated only on the final examination (Table. 1).

4. Statistics

Paired T-test will be conducted to identify differences between the clinical scores at the baseline and the subsequent follow-ups for the different conditions investigated (*i.e.* caries score, erosion score) (24).

Exploratory analysis of the data extracted from the 3D scans will be conducted and compared to the clinical scores. Pearson correlation coefficients between the clinical scores and scores obtained from the 3D scans will be calculated. Paired t-test will be conducted to compare the number of lesions per patient (*i.e.* caries, tooth wear) that will be detected with the 2 different methods (scanning and clinical-radiographic examination).

All statistical analysis will be conducted using a 95% level of confidence.

Information regarding the sample size calculation using power analysis is provided on the following paragraph (§5. Research subjects - Sample size calculation)

5. Research subjects

The participants in this research project will be adolescents (12-16 years old) and young adults (18-19 years old) in Denmark and in Greece respectively.

As previously mentioned, this project will assess the ability of the intraoral scanner combining fluorescence to detect and monitor initial changes in the dental hard tissues, with special focus on caries: the most prevalent oral disease. The most important benefit expected by using the fluorescence method is the detection of initial lesions on dental surfaces directly exposed to the mouth. Fissure lesions in permanent posterior teeth usually appear in the long-lasting period of tooth eruption, *i.e.* from when the tooth first appears in the mouth until it contacts with the opposite dentition (28). Eruption of the first permanent molar starts around the ages of 6-8 years, the second molar at 12-14 years (28) and the third molar at 17-18 years. During the eruption period, the posterior teeth are at a higher risk for developing fissure caries. For the second permanent molars, this period can last up to 27 months form the first appearance in the mouth (~12 years old) (29) though for the third molars this period is usually longer.

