The initial state of the caries lesion is short-lived before progression of the disease. In older patients, caries lesions in fissures are either found at more advanced stages or they have already been treated by the dentist (*i.e.* sealed, filled or extracted as in the case of third molars) (28). Although initial caries lesions can be found in older patients, such initial lesions are located on the surfaces between the teeth, which are not visible to the intraoral scanner and therefore cannot be detected using this method.

For these reasons, the age group is set from 12 to 19 years. It is necessary to conduct the study on this group of young people, as the study is expected to benefit them directly. The same benefits are not expected if the study is conducted in older adults.

The early diagnosis of initial lesions in the young participants is more beneficial as it will allow the implementation of preventive measures to stop the progression of the disease. This will decrease the complexity of the treatments needed in the target group, as the initial lesions can be treated with minimal or non-invasive approaches. Thus, the economic burden for the state regarding treatment expenses of the adolescents and the individual costs related to future dental treatment will be reduced.

Inclusion criteria:

- Young people (12-19 years old) without chronic diseases.

Exclusion criteria:

- Participants in need of complex dental treatment (*e.g.* extensive restorative work, extractions, prosthetic treatment).
- Participants using partial/complete removable dentures or other appliances (*i.e.* orthodontic devices).

Sample size calculation

Caries data was used in order to calculate the desirable sample size for the current study, as that is the most prevalent oral disease in young patients and is widely investigated in epidemiological studies (1). Therefore, data regarding initial caries lesions was used for the sample size calculation, assuming that the new method will aid dentists to detect significantly more initial caries lesions compared to traditional methods.

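### A higher scan count would not by itself show earlier detection, because no planned analysis tests whether scan-only lesions are real

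*Combined protocol and SAP*

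**What the plan says.** Hypothesis 2 (section 2a) is about timing: the scanner "will aid dentists to identify changes in the dental hard tissues at earlier stages than the traditional diagnostic methods".

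The sample size (section 5) rests on a count instead, "assuming that the new method will aid dentists to detect significantly more initial caries lesions compared to traditional methods", with a target effect of 1 lesion.

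Section 4 names three analyses that bear on the scanner:
- A general one: "Exploratory analysis of the data extracted from the 3D scans will be conducted and compared to the clinical scores".
- An association: "Pearson correlation coefficients between the clinical scores and scores obtained from the 3D scans will be calculated".
- A test: "Paired t-test will be conducted to compare the number of lesions per patient", the lesions being those "detected with the 2 different methods (scanning and clinical-radiographic examination".

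The one longitudinal test in section 4 compares clinical scores at baseline and follow-up; scan findings do not enter it.

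On the comparator, the background (section 2b) says that "a number of initial lesions typically remain unnoticed when visual examination alone is used" and that radiographs are insensitive to early enamel demineralization. It also says that the scanner cannot examine approximal surfaces.

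The examination, scan and bitewings done at baseline are planned again at 1 year (section 3, Table 1).

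**The concern.** The hypothesis concerns earlier detection, but the test concerns number. The number of scan positives can rise for two reasons: the scanner finds true lesions that the comparator has not yet seen, or it calls sound surfaces positive. Each such call adds one to the participant's count, so the paired t-test cannot tell them apart.

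Nothing else in the plan separates them. The comparator cannot settle a scan-only call at the same visit, because by the protocol's own account it overlooks this kind of lesion. No third method, adjudication, surface-by-surface cross-classification, sensitivity, specificity or predictive value is planned. No analysis follows scan-only surfaces to 1 year.

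At stake is the interpretation of a positive result. The early-diagnosis benefit claimed in sections 5 and 11 requires the extra calls to be real lesions. A significant count difference would not establish that.

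**Working it through.** **1. The plan's own figure.** Inputs from section 5: SD 1.23, difference 1 lesion, power 90%, significance level 5% (taken as two-sided). For two means, n per group = 2 × SD² × (1.960 + 1.282)² / difference² = 2 × 1.5129 × 10.51 / 1 = 31.8, so 32 per group and 64 in total. This matches the stated 64. With 10% added, 64 × 1.10 = 70.4, or about 70. The study is therefore sized on a difference in mean counts, not on accuracy.

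**2. False positives that equal the target effect.** The documents give no number of surfaces. Assume 50 to 72 exposed surfaces per participant, where 72 = 28 teeth × 2 (buccal and lingual) + 16 posterior occlusal. Break-even excess rate = 1 lesion / surfaces:
- 72 surfaces: 1/72 = 1.39%
- 60 surfaces: 1/60 = 1.67%
- 50 surfaces: 1/50 = 2.00%

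If the effect is read as 30% of 3.08 = 0.924 lesions, the range is 0.924/72 = 1.28% to 0.924/50 = 1.85%. These rates require a count confined to exposed surfaces and scanner sensitivity no lower than the comparator's. They translate into a scanner specificity of 98% to 99% only if comparator specificity is near 100%.

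**3. If approximal lesions stay in the comparator count.** The scanner must then replace them before it can show an excess. The approximal share is assumed:
- One third of 3.08 = 1.03, so 2.03 false positives are needed: 2.8% (72 surfaces) to 4.1% (50).
- One half of 3.08 = 1.54, so 2.54 are needed: 3.5% to 5.1%.

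**4. Excess needed for significance alone.** With 64 pairs, the critical mean difference is 1.998 × SD of the difference / 8, where SD of the difference = 1.23 × √(2(1 − ρ)). For ρ = 0 this is 1.998 × 1.74 / 8 = 0.43 lesions; for ρ = 0.8 it is 1.998 × 0.78 / 8 = 0.19. The correlations are assumed. The SD of 1.23 is described as across municipalities and may not be the between-patient SD.

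**5. Does the Pearson correlation protect?** Simulation: 2,000 trials per setting, 64 patients, comparator counts with mean 3.08 and SD 1.23, every comparator lesion true and visible to the scanner, and a scanner that finds no true lesion beyond the comparator. Surfaces, sensitivity (relative to the comparator) and specificity are assumed.

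| Surfaces | Sensitivity | Specificity | Mean excess | t-test favours scanner | Mean r |
|---|---|---|---|---|---|
| 40 | 100% | 95% | 1.84 | 100% | 0.67 |
| 70 | 100% | 98% | 1.34 | 100% | 0.73 |
| 70 | 80% | 98% | 0.72 | 99.2% | 0.59 |
| 20 | 60% | 95% | −0.38 | 0.1% | 0.48 |

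In the first three rows a scanner with no true gain is favoured almost always while the correlation stays moderate to high. The last row shows that over-calling does not always produce an excess: with few surfaces and low sensitivity, missed lesions outweigh false positives.

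**The case against.** Five points can be made for the plan.

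- *No success rule is stated.* A reader might infer that the protocol declares the scanner better if it finds more lesions. It does not: the sentence in section 5 is a planning assumption, and section 4 introduces the scan work as exploratory. This stands, and the claim must be one of implication. But no other criterion for hypothesis 2 is given.
- *The scan scores are also correlated with the clinical scores.* True, but a correlation measures association between scores. It cannot validate surfaces that the comparator calls sound.
- *The unrestricted count may work against the scanner.* The comparator includes bitewings, and section 4 does not confine the count to exposed surfaces. This stands. It raises the false-positive rate needed, and it is a reason to restrict the comparison, but it does not show that scan-only calls are real.
- *Participants are not shown to be at risk of mislabelling.* A reader might infer that young people would be classed as diseased on scan results. Section 3 bases risk grouping on the clinical findings, diet history and hygiene questionnaire and does not name the scan. The documents do not support that reading; the concern is about the conclusion drawn.
- *Follow-up is an imperfect arbiter.* The same comparator is used a year later. Fissures of erupting molars are at higher risk, so a scanner that merely flags fissures would appear to predict conversion. Referral for treatment, preventive care and drop-out also intervene. These points stand. They limit the check to supportive evidence and require allowance for surface type.

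**Conclusion.** The concern holds as a gap in the analysis plan. The sample-size assumption and the sole between-method test imply that a higher scan count supports the scanner, yet a higher count alone does not support hypothesis 2, and no planned analysis can show whether scan-only lesions are real.

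The gap itself follows from the text; its size is only illustrative. The 1.4% to 2.0% figure depends on all the conditions in step 2 of the working, and it rises to about 2.8% to 5.1% if one third to one half of the comparator's lesions are approximal. A reader might go further and infer that the scanner does over-call, or that 98% to 99% specificity would always produce the effect. The documents give no accuracy data for the scanner or the comparator, so neither inference is supported.

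The change should be made, because it is cheap and bears directly on the study's second hypothesis.

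**What to change.** In section 4:

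1. Restrict the between-method comparison of lesion counts to exposed surfaces (smooth free surfaces and occlusal fissures).
2. Add a surface-level analysis. Among exposed surfaces found sound by the comparator at baseline, compare baseline scan-positive with scan-negative surfaces on the proportion clinically (ICDAS ≥ 1) or radiographically positive at 1 year. Stratify by or adjust for surface type (fissure versus smooth, erupting molars). Give the difference or ratio with confidence limits that allow for clustering within participant.
3. Chart the 1-year clinical findings without opening the baseline scan. Report surfaces treated in between as a separate category. Limit the analysis to participants with a 1-year examination; at the expected 10% drop-out that is about 70 × 0.9 = 63.
4. State the interpretation in advance. Higher conversion of scan-positive surfaces is supportive evidence of earlier detection, not proof. Without it, report the count difference as *more positive calls*, not as more or earlier lesions.

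Cost: new wording in section 4 and a surface-level data file; no extra visit, procedure or participant. Downside: arrested lesions and interim preventive care reduce conversion, so the check is conservative and its confidence limits may be wide.

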For the sample size calculation, data collected by the Central Odontology Register of the Danish National Board of Health (Sundhedsstyrelsens Centrale Odontologiske Register SCOR) during the year 2017 from municipal dental clinics at 98 different municipalities in Denmark was used. According to the data, an average of 3.08 initial lesions, with a standard deviation of 1.23 were identified on 15-year old patients at the different municipalities. In this study, the desirable power was set on 90%, the level of significance on 5% and the effect size on 30% (1 lesion). By applying these parameters, the sample size was calculated to be 64 adolescents. Nevertheless, as a 10% drop-out is expected for this type of study, the final number of participants to be included in the study should be 70.

6. Risks, side effects and shortcomings in short and long term

Risks

This study will be conducted on healthy persons, on whom the procedures followed in this study are assumed to have a negligible risk.

No risk is related to the clinical visual examination.

Regarding the 3D intraoral scanning procedure, if the scan quality is poor and thus the scan is not useful for the research objectives, the scanning procedure should be repeated. This is of no risk for the patient but represents the inconvenience of a delay of the dental visit.

For the scanning using blue light (wavelength 415nm) possible risks exist. For the participant, light irritation of the mucosa and lips may result from a local, acute overexposure to the strong blue light. This irritation, though, is mild and temporary. For the operator, possible harm to the eyes, especially on the lenses and the retinal tissues, may be caused by long-term cumulative exposure to blue light. These risks are not particular for this specific intraoral device but are

common to any dental equipment that uses blue light. Having these risks in mind, the equipment will be used properly and with care: the exposure time will be limited to 15 seconds per tooth and direct exposure to mucous membranes will be avoided. The equipment will be started only after it has been inserted into the patient's mouth. The operator will avoid looking directly into the mouth and instead will look on the computer screen during the scanning procedure. Eye-protection goggles filtering light under 500 nm are suggested to be used by the operator.

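### The SD of 1.23 behind the sample size appears to describe municipality averages rather than persons, and the planned paired test needs a different SD, so the stated 90% power is unsupported in either direction.

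*Combined protocol and SAP*

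**What the plan says.** Section 5 (Research subjects, Sample size calculation) uses 2017 Danish register data "from municipal dental clinics at 98 different municipalities in Denmark was used". It reports "an average of 3.08 initial lesions, with a standard deviation of 1.23 were identified on 15-year old patients at the different municipalities". The remaining inputs are these: "the desirable power was set on 90%, the level of significance on 5% and the effect size on 30% (1 lesion"). The result is that "the sample size was calculated to be 64 adolescents", and then, "as a 10% drop-out is expected for this type of study, the final number of participants to be included in the study should be 70".

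The opening of section 5 describes the participants as "adolescents (12-16 years old) and young adults (18-19 years old) in Denmark and in Greece respectively". The criteria exclude chronic disease, removable dentures or orthodontic and other appliances, and need for complex treatment such as "extensive restorative work, extractions, prosthetic treatment".

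For the comparison of scanning with the clinical-radiographic examination, section 4 (Statistics) says: "Paired t-test will be conducted to compare the number of lesions per patient". The plan gives neither an SD of within-patient differences nor a correlation between the two methods.

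**The concern.** Three things do not line up.

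- **Level of the SD.** The planned analysis counts lesions in each person. The planning SD is reported across municipalities, and it is small for a person-level count with mean 3.08. Section 3 sorts participants into low, moderate and high risk, so the plan itself expects people to differ. Such differences push a count's variance above the Poisson value, not below it.
- **Coverage.** The register figures are for 15-year-olds in Denmark only. No planning figure covers the Greek 18-19 group or the other Danish ages. Section 5 itself argues that fissure caries risk follows the stage of tooth eruption, so a single-age figure cannot be assumed to hold from 12 to 19.
- **Quantity needed.** A paired t-test depends on the SD of the difference between methods within a patient. Neither a municipality-level SD nor a person-level SD supplies that without a correlation.

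At stake is whether 90% power is a justified claim for the people enrolled and the test planned.

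**Working it through.** **Inputs.** From section 5: mean 3.08, SD 1.23, difference 1 lesion, power 90%, significance 5% (taken as two-sided), N = 64, drop-out 10%, final N = 70. From section 4: paired t-test within patient. Assumed, because the documents give no values: person-level SDs of 1.75, 2.5 and 3.08, equal for both methods, and between-method correlations (ρ) of 0, 0.5 and 0.7.

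**1. Reproducing the plan's 64.** The plan names no formula. The normal-approximation formula for two independent groups gives

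n per group = 2 × 1.23² × (1.960 + 1.282)² / 1² = 31.8, rounded up to 32, so 64 in total.

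This matches exactly. A paired calculation with 1.23 as the SD of differences gives 18 pairs and does not match. Using 30% of 3.08 = 0.924 in place of 1 lesion gives 2 × 38 = 76 and does not match either. So 1.23 seems to have entered as the SD of individual values in two separate groups.

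Drop-out: 64 × 1.10 = 70.4, near the stated 70. With 70 enrolled, 70 × 0.9 = 63 are evaluable.

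**2. Is 1.23 plausible between persons?** Variance/mean = 1.23² / 3.08 = 1.513 / 3.08 = 0.49. A Poisson count with mean 3.08 has SD √3.08 = 1.75. A person-level SD of 1.23 would mean counts about half as variable as pure chance, in a population the plan divides by risk. Averages over many children vary less than individual children do, so municipality averages are the more natural reading.

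**3. What the planned test requires.** With noncentral t, two-sided 5% and a difference of 1, 90% power needs an SD of differences of at most 2.43 with 64 pairs, or 2.41 with 63.

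**4. Power over the assumed range.** SD of differences = SD × √(2(1 − ρ)). For example, SD 2.5 with ρ = 0.5 gives 2.5 × 1 = 2.5, just above 2.43, and power of 88%. At 64 pairs:

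| Person-level SD (assumed) | ρ = 0 | ρ = 0.5 | ρ = 0.7 |
|---|---|---|---|
| 1.75 | 89% | 99% | >99% |
| 2.5 | 61% | 88% | 98% |
| 3.08 | 44% | 73% | 91% |

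With 63 pairs each value is lower by about one percentage point or less.

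**5. Why correcting the test alone is not enough.** If 1.23 is kept as the person-level SD, the SD of differences at ρ = 0 is 1.23 × √2 = 1.74, and 64 pairs give over 99% power. That would be false reassurance if 1.23 is a municipality-level figure.

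**The case against.** The case for leaving the plan alone has real content.

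- *Fifteen-year-olds are eligible.* They fall inside the Danish 12-16 range, and register data for one age within the range are an ordinary planning source. This stands. A reader might infer that the figures come from the wrong population; the documents support only that they are narrow. The exclusion of complex treatment need could even trim high counts and reduce the person-level SD.
- *The documents never say 1.23 is a between-municipality SD.* This also stands. Poisson is a benchmark, not a lower bound. The reading is a strong inference from the wording and the arithmetic, no more.
- *The study may be adequately powered.* A reader might infer underpowering, particularly after putting larger SDs into the formula that reproduces 64: two groups of 32 give 61% power at SD 1.75 and 35% at SD 2.5 (noncentral t). But the trial does not compare two independent groups. Each participant is examined by both methods in the same mouth, so a substantial correlation is plausible, and in the paired table power is close to 90% or above in five of nine cells and at 88% in a sixth.
- *The mean does not drive N once the difference is fixed at 1 lesion.* Correct for the arithmetic. The mean matters only as the basis for calling 1 lesion a 30% effect.

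None of this supplies the missing quantity. The plan still gives no SD of within-patient differences, and the one SD it gives is probably at the wrong level.

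**Conclusion.** The concern holds in a limited form: the 90% power is unsupported, and the direction of the error cannot be determined. The planning SD is very probably not person-level, covers one age in one country, and is not the quantity that the planned paired t-test uses. Across the assumed SDs of 1.75 to 3.08 and correlations of 0 to 0.7, power at 64 pairs runs from 44% to over 99%, and 90% is reached only where the SD of differences is 2.43 or less. These SDs and correlations are illustrations; none comes from the documents.

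Two further unknowns widen the uncertainty. Section 2b (Background) says that the scanner cannot examine approximal surfaces, and section 5 does not say whether the register count of 3.08 includes them. No planning value of any kind exists for the Greek participants.

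The point merits correction because it concerns the figure on which the sample size rests and is cheap to repair.

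**What to change.** In section 5, Sample size calculation:

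1. State whether 1.23 is an SD between persons or between municipality averages, and whether the count includes approximal surfaces. Do not use 1.23 as a person-level SD unless it is confirmed to be one.
2. Replace the single 90% with the power of the paired t-test for a 1-lesion difference at 63-64 evaluable participants (not the 70 enrolled). Give it as a range over a stated person-level SD and between-method correlation, and include the limiting SD of differences (2.43 with 64 pairs, 2.41 with 63).
3. Use person-level register values for the enrolled Danish ages if they can be obtained. Otherwise label the SD as an assumption. Give an explicit assumed range for the Greek 18-19 group.
4. State that the planning data are limited to Danish 15-year-olds.

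The cost is a register query or a stated assumption, plus a few reworded sentences. No change in enrolment is asked for. The downside is that the stated power may become less favourable.
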